intervention fidelity; and maximize participant retention. Detailed records on recruitment, session attendance, and homework completion will be kept throughout the intervention. Consistent with Consolidated Standards of Reporting Trials (CONSORT) guidelines, we will obtain data to determine (1) the number of participants who reported moderate or greater symptom ratings, or who have impairments in one or more cognitive domain, from the baseline assessment; (2) the number of participants referred to the study, (3) the number of participants screened by research staff for study eligibility, and (4) the number enrolled in and completing all aspects of the study including treatment sessions and assessments. We will ascertain reasons for unsuccessful recruitment, ineligibility, and unsuccessful enrollment of eligible Veterans. In addition, we will collect data on the intensity of outreach needed to recruit and enroll participants (e.g., number of phone calls required before Veterans complete eligibility screening, number of "no shows" for eligibility screening appointments) and length of time between initial recruitment attempt, eligibility screening, and completion of the pre-intervention assessment. Participant Retention will be measured by the proportion of participants who complete follow-up assessments within two weeks of the target date. Treatment satisfaction will be assessed by the Client Satisfaction Questionnaire (CSQ8).

Functional and Clinical Variables: We will use similar assessment procedures as in the Aim 1 study to assess cognitive and functional domains most strongly associated with PTSD (details listed in the table below). We will examine sleep and mental health symptoms (including PTSD and depression) not directly targeted by CCT to examine comparability to TAU. Assessments will take approximately 1.5 hours and will occur at baseline, post-treatment, and 6-month follow-up for both groups.

Measure	Construct Assessed			
Objective Cognitive Functioning (Neuropsychological Tests)				
Test of Premorbid Functioning (ToPF)	Verbal abilities; estimate of premorbid cognitive functioning			
California Verbal Learning Test (CVLT-II; Delis et al., 2000)	Verbal learning and memory, forced choice validity			
Wechsler Adult Intelligence Scale (WAIS-IV) Digit Span & Coding subtests (Wechsler, 2008)	Attention, working memory, processing speed, reliable digit span validity			

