Randomization and Blinding: All eligible participants will be randomized to either the CCT or TAU group. Randomization tables will be prepared by the study statistician at the beginning of the study and assignments to CCT or TAU will be based on the randomization table. New participants will be allocated to the current group awaiting randomization. Once group membership reaches 6 participants, the group will be randomized by the statistician. We will employ a system of adaptive randomization, weighted to achieve the desired proportion of participants in each condition, managed by the statistician. Randomization will be implemented by the study coordinator in coordination with the statistician who will monitor randomization procedures. Because of the small sample size and number of study personnel in this pilot RCT, it might not be feasible to blind the assessor to participant group status if the assessor is also co-facilitating CCT groups with [name], though this type of blinding will be implemented if possible.

Data Analysis: Rates of recruitment, retention, and participation will be calculated, and we will compare participant characteristics at baseline by group (CCT vs. TAU). We will conduct intent-to-treat analyses to compare change from baseline to 3-month follow-up within and between groups.

Study Feasibility Analyses: Descriptive statistics will characterize the feasibility of recruiting and retaining Veterans. Recruitment will be deemed feasible if we successfully screen for eligibility 50% of Veterans referred to the study and enroll 75% of screened Veterans who meet all study inclusion criteria. Retention will be deemed successful if we achieve 80% completion for post-treatment assessments. Chi-square tests of association for categorical variables and t-tests for continuous variables will compare demographic and clinical characteristics of successfully versus unsuccessfully recruited and retained Veterans to identify characteristics of participants who may require more intensive recruitment or retention efforts in a future trial.

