Clinical and Functional Outcome Analyses: An additional goal of clinical and functional outcome data from this pilot RCT is to obtain effect size estimates to prepare for a future fully powered RCT. Because estimating effect sizes in small pilots is fraught with limitations and should not be used as a sole estimate (e.g., Kraemer et al., 2006), we will compare obtained effect sizes to those obtained for participants with PTSD in our CCT for mild TBI trial. We are not relying on the TBI data alone, however, because of the potentially significant differences in Veterans who do and do not have a history of TBI. Therefore, though we will conduct multivariate analyses of pilot data and examine the statistical significance of within and between group differences, we will focus on obtaining effect size estimates to prepare for a future trial. Because of the small sample size, we will examine data for trends to plan for future analyses in a fully powered RCT. To evaluate the proportion of Veterans with early discharges from CCT, we will conduct mixed models for binary outcomes. We will plan for an underpowered pilot trial, though will use the obtained effect sizes to estimate statistical power and needed sample size for the fully powered RCT RR&D Merit proposal in year 4 of the CDA. We will also use appropriate assumptions for planned statistical tests when calculating estimated power.

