In this pilot study, we will first examine descriptive statistics, and conduct tests of normality and homogeneity of variance for variables included in repeated measures analyses. We will examine missing data for all variables and dropout rates in order to plan for a future RCT. though will not conduct multiple imputation or other missing data techniques for this pilot study. We will, however, conduct intent to treat analyses, analyzing data from all randomized participants assigned to CCT versus TAU groups, rather than only including completers. Primary outcome analyses will be multilevel models to compare the change over time in cognitive, mental health, functioning, and QOL outcomes for Veterans in the CCT versus TAU groups. If the sample size is too small to run multilevel models, we will run alternative methods such ANOVAs which are more feasible with smaller samples. We will examine how much symptoms change, comparing changes across groups, and also examine clinically significant change in self-reported functional and clinical outcomes. We will compare the change in proportions of Veterans who fall within in "clinically significant impairment" ranges on objective cognitive performance measures before and after CCT versus TAU, characterizing cognitive functioning deficits according to cognitive domains. Because of the small sample size in this pilot RCT, these analyses will rely heavily on descriptive statistics including identifying individuals who score within clinically impaired ranges on objective testing, and who score above clinical cutoffs on self-report measures. Multilevel models or repeated measures analysis of covariance (ANCOVA) models will examine potential moderators including validity tests, service connection status and percent, number of sessions attended, comorbid mental health diagnosis such as PTSD, and demographic variables.

Study Population and Subject Identification/Recruitment

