Participants will be at least 36 (and up to 48) Veterans weighted with more CCT participants (approximately 4-5 CCT groups with 6 Veterans each) than controls (12-18 TAU participants, grouped for randomization piloting purposes into 6-Veteran participants in each of 2 groups). Veterans of all genders, races, and ethnicities will be eligible for this study. We have estimated enrollment for gender, race, and ethnicity based on the recent CCT for mild TBI study, assuming similar demographic proportions. Eligibility will be established by current Mental Health or PTSD Clinic provider and CPRS chart review and will be confirmed by the Veteran during the initial phone call. Eligible Veterans (1) must meet DSM-5 criteria for PTSD based on PTSD or Mental Health Clinic intake assessment or PTSD diagnosis at most recent Mental Health/PTSD clinic visit if intake was completed over 6 months prior to study participation; (2) are patients in the PTSD specialty clinic or Mental Health clinic with a current mental health provider who is willing to provide TAU if randomized as such; (3) prior EBP treatment within the past 2 years confirmed by patients, their current Mental Health or PTSD clinic provider, and a review of CPRS records; (4) do not have a history of TBI of any severity; (5) are able to provide informed consent; (6) are English speaking; (7) are able to travel to the clinics for appointments; (8) do not have auditory or visual impairments that would compromise assessments; (9) do not meet criteria for a substance dependence disorder with less than 30 days abstinence; (10) do not meet criteria for bipolar disorder or psychotic disorders; (11) do not have active suicidal intent indicating significant clinical risk (which would suggest that a treatment specifically targeting this intent was indicated); (12) do not have a major medical condition likely to significantly impact cognitive functioning such as stroke, multiple sclerosis, Parkinson's, brain tumor, or congestive heart failure; (13) are not currently participating in any type of brain stimulation treatment; and (14) are between the ages of 18 to 75 years old. To maximize the generalizability of the study and ensure that we are testing CCT with a typical PTSD Veteran population, exclusion criteria are minimized (e.g., there are no medication exclusion criteria, and Veterans with comorbid depression or anxiety disorders will be included). Current cognitive functioning deficits are also required for participation, and chart review and NSI screening will be implemented for this study.

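### Does the single 80% retention criterion need a separate threshold for each arm, given that allocation favours CCT?

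*Combined protocol and SAP*

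**What the plan says.** The success rule is in Study Feasibility Analyses: "Retention will be deemed successful if we achieve 80% completion for post-treatment assessments". It names no arm. The Feasibility and Acceptability section defines the measure in the same undivided way: "Participant Retention will be measured by the proportion of participants who complete follow-up assessments within two weeks of the target date".

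The Inclusion/Exclusion Criteria section describes enrolment as "weighted with more CCT participants (approximately 4-5 CCT groups with 6 Veterans each) than controls", with 12-18 TAU participants. The total is 36 to 48.

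Other text bears on retention:

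- Feasibility and Acceptability commits, under CONSORT, to record "the number enrolled in and completing all aspects of the study including treatment sessions and assessments".
- Data Analysis says that retention rates will be calculated. Its reference to CCT versus TAU attaches to baseline characteristics.
- Study Feasibility Analyses plans chi-square and t-tests of retained against non-retained Veterans. Assigned arm is not on the list of characteristics.
- Clinical and Functional Outcome Analyses has one arm-specific item: "To evaluate the proportion of Veterans with early discharges from CCT, we will conduct mixed models for binary outcomes". That concerns leaving treatment, not missing an assessment.
- The same section says: "We will examine missing data for all variables and dropout rates in order to plan for a future RCT". It adds that the team "will not conduct multiple imputation or other missing data techniques for this pilot study", and that all randomized participants will be analysed in the CCT and TAU groups.
- Participant retention/Dropout Minimization reports retention above 90% in recent CCT trials and describes retention efforts that apply to every enrolled Veteran, whatever treatment is being received.

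**The concern.** A pooled proportion under unequal allocation is driven by the larger arm. Here that is CCT, so the trial could meet its only retention criterion while a large part of the small TAU arm goes unassessed. Feasibility is Aim 1, and the future trial compares CCT with TAU, so whether controls return for assessment is a real feasibility question. Aim 2 draws on the same people: effect sizes from this pilot feed the next sample-size calculation, and no missing-data technique will compensate for uneven loss. No sentence in the plan states that retention will be shown by arm, so the word *successful* could hide a weak control arm.

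**Working it through.** **Inputs.** CCT 4-5 groups of 6, so 24-30; TAU 12-18 (Inclusion/Exclusion Criteria). Threshold 80% (Study Feasibility Analyses). Denominator taken as all randomized; the plan does not state one, so this is an assumption.

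**The plan's total.** 4 × 6 + 12 = 36 and 5 × 6 + 18 = 48. Both match the stated 36 to 48.

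**Worst-case bounds.** Completers needed = 0.80 × N rounded up. Allowed loss L = N − needed. If all losses fall in one arm, the loss in that arm is L divided by its size.

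| CCT/TAU | N | Needed | L | CCT share | Max CCT loss | Max TAU loss |
|---|---|---|---|---|---|---|
| 24/12 | 36 | 29 | 7 | 67% | 7/24 = 29% | 7/12 = 58% |
| 30/12 | 42 | 34 | 8 | 71% | 8/30 = 27% | 8/12 = 67% |
| 24/18 | 42 | 34 | 8 | 57% | 8/24 = 33% | 8/18 = 44% |
| 30/18 | 48 | 39 | 9 | 63% | 9/30 = 30% | 9/18 = 50% |

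The two loss columns cannot occur together; they are the same 7-9 people divided by different arm sizes. The enrolment end points (24/12 and 30/18) give 29-30% against 50-58%. The wider ranges need the two mixed layouts. The Inclusion/Exclusion Criteria section also mentions only 2 TAU groups of 6, which is 12; at that size the TAU bound is 58-67%.

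**At the retention the team has seen before.** Over 90% overall means at least 33/36, 38/42, 38/42 or 44/48. With CCT complete, TAU is then at least 33 − 24 = 9/12, 38 − 30 = 8/12, 38 − 24 = 14/18 or 44 − 30 = 14/18. TAU is at two-thirds or better in every layout.

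**How often a pass would hide weak TAU retention.** This is the exact binomial chance that the pooled rule is met while observed TAU completion is below two-thirds (7/12 or less, 11/18 or less). True rates are assumed, because the documents give none by arm. Order: 24/12, 30/12, 24/18, 30/18.

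- 95% CCT, 60% TAU: 35, 42, 18, 28%
- 90% CCT, 60% TAU: 19, 24, 7, 12%
- 95% CCT, 80% TAU: 3-6%
- 80%, 85% or 90% in both arms: under 1%

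**What a by-arm floor would do.** Suppose each arm also had to reach two-thirds (TAU 8/12 or 12/18).

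- At 95% CCT and 60% TAU, the trial still passes 35-43% of the time.
- At 95% CCT with TAU truly at two-thirds, it passes 58-63%, so it fails 37-42%.
- Requiring 80% in each arm would need TAU at 10/12 or 15/18, so the verdict would turn on a third or fourth lost Veteran.

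**Effect on precision.** The approximate 95% half-width for a between-arm difference in SD units is 1.96 × √(1/n₁ + 1/n₂), unadjusted and ignoring group clustering. For 29/36 split 24/5 it is 0.96; split 19/10, it is 0.77. The 24/5 split is remote: at 95% and 60% its chance is 0.95²⁴ × P(5 of 12) = 0.29 × 0.10, about 3%. At the floor's own margin, 22/7 gives 0.85 and 21/8 gives 0.81, a gain of about 0.04 SD.

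**The case for a change.** The strongest case for a change is that the criterion is the only prespecified statement on retention success, that it can be met with as few as 4 of 12 controls assessed, and that no sentence promises a split by arm. The over-90% figure comes from other trials, is not given by arm, and was not the level the sponsor set as success. A pass with TAU below two-thirds does not need perfect CCT retention: 22/24, 27/30, 23/24 or 28/30 is enough (90-96%). One extra sentence would cost nothing in data, and a two-thirds floor would lower the pass chance by under 1 point when both arms truly retain 80%, 85% or 90%.

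The reading of the text and the arithmetic stand. What does not stand is the step to a defect. Even at the extreme, a pass requires some TAU retention (4/12 to 10/18), so the label never describes CCT alone. The two-thirds figure has no source in the documents, and in 12-18 people it separates good from poor retention weakly. Reporting completion by arm is sensible, but it is detail that the planned counts and analyses already lead to.

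**Conclusion.** No change is needed. The pooled 80% rule does constrain TAU less than CCT: at worst 50-58% TAU loss against 29-30% CCT loss at the enrolment end points, and 44-67% against 27-33% across all four layouts. Those bounds assume an all-randomized denominator and all losses in one arm. They are not predictions, and at overall retention above 90% TAU is at 8/12 or 14/18 at the least.

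The plan attaches no stop or go decision to the label, describes the pilot as underpowered by design, and says pilot effect sizes should not be the sole basis for planning. An analyst following CONSORT, examining dropout and fitting CCT-versus-TAU models on all randomized Veterans will have completion by arm and would ordinarily show it beside the 80% result. A numerical floor for the smaller arm would trade a simple descriptive benchmark for one that turns on one or two people, with little gain.

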Study setting, sample size, and recruitment feasibility: The proposed study is conducted at a single site. We propose to enroll at least 36, and up to 48, total Veterans in this pilot RCT. Because our primary purposes are to examine feasibility of this clinic-based research and acceptability to Veterans with PTSD and estimate effect sizes for a future fully powered RCT. achieving adequate statistical power is not a primary concern of this pilot clinical trial. Results from this pilot RCT with a sample size of 36 to 48, combined with comparisons to similar studies of CCT with other Veteran groups (e.g., those with mild TBI history), will provide adequate information on expected effect size to allow for estimations of statistical power for a future RR&D Merit proposal of a fully powered RCT. VHAPORHCS Mental Health and PTSD clinics will serve as primary sites for study recruitment, assessment, and intervention activities. We will work with the Public Affairs Office to post IRB approved study flyers in VHAPORHCS Mental Health and PTSD clinics and nearby elevators as well as the main hospital. The flyers provide information about the study and will help notify Veterans of the opportunity to participate in this study. Eligibility and recruitment procedures used to identify Veterans who report residual cognitive functioning deficits following recent (past year) treatment for PTSD at the Portland VA will be used to recruit Veterans for this pilot trial. Veterans who have participated in PTSD treatment and report cognitive functioning deficits on the Neurobehavioral Symptom Inventory (NSI; moderate cognitive symptoms or greater on any cognitive functioning item), will be recruited from the clinics.

CDW: If needed to achieve recruitment goals, we will also access the VA's Corporate Data Warehouse (CDW) and use ICD-10 codes to identify Veterans with recent (past year) Portland VA mental health or PTSD clinic treatment for PTSD. NSI data is also available for some Veterans in CPRS and Veterans with elevated NSI scores or neuropsychological evaluations

9

will be prioritized for recruitment. The CDW will be used to identify potentially eligible Veterans. The Veterans' clinicians will be contacted to ask them if they would like to refer these identified Veterans to the study. If the clinician wants to refer a Veteran to the study, this will be documented and the IRB approved recruitment procedures for a referred Veteran will then be followed.

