to complete follow-up assessments, advance participant reminders of upcoming assessments, scheduling assessments near the target date at times that are convenient for participants, providing reminder calls 1-3 days prior to the scheduled assessment, and promptly rescheduling missed assessment appointments. We will attempt to retain all enrolled Veterans in the study, regardless of ongoing participation in CCT or other interventions as part of TAU. In our prior research, all Veterans who initiated CCT completed the intervention. For Veterans who discontinue treatment and who express discomfort returning to the clinic to complete follow-up assessments, accommodations will be made to ensure Veterans have the opportunity to continue study participation (e.g., assessment completion via VVC or telephone or at other VAPORHCS locations). We will ensure that participants are appropriately reimbursed for time and travel, paying participants \$50 for each assessment. Recent trials of CCT in VA clinics conducted by Drs. [name], [name], and [name] have exceeded 90% retention.

Inclusion/Exclusion Criteria

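### Early discharge from CCT is better summarised by a proportion with an exact interval than by a mixed binary model, because 24–30 Veterans should give few events and possibly none.

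*Combined protocol and SAP*

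**What the plan says.** The first paragraph of Clinical and Functional Outcome Analyses states: "To evaluate the proportion of Veterans with early discharges from CCT, we will conduct mixed models for binary outcomes". It does not define early discharge. It names no random effect, covariates or comparator, and no rule for few or zero events.

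The available data follow from Inclusion/Exclusion Criteria, which plans "approximately 4-5 CCT groups with 6 Veterans each" in the CCT arm and "12-18 TAU participants, grouped for randomization piloting purposes into 6-Veteran participants in each of 2 groups" in the control arm. Under Participant retention/Dropout Minimization the team reports: "In our prior research, all Veterans who initiated CCT completed the intervention". The same section says that its recent CCT trials "have exceeded 90% retention".

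Other parts of the plan touch the same quantity. Data Analysis promises recruitment, retention and participation rates. Feasibility and Acceptability provides for attendance records and a count of those who complete the treatment sessions. The second paragraph of Clinical and Functional Outcome Analyses says dropout rates will be examined, and it allows ANOVA-type methods if the sample is too small for multilevel models.

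**The concern.** TAU participants receive no CCT and cannot be discharged early from it, so the target is a proportion in one arm. A mixed model has to estimate that proportion and a between-group variance from 4–5 groups of six. If the earlier CCT experience repeats exactly, there are no events, and a logistic model fitted by maximum likelihood has no finite estimate. Full completion would be a favourable finding, yet it is the one result the named method cannot report with an interval. The small-sample fallback does not help: it follows the sentence on change-over-time models, and ANOVA does not suit a sparse yes/no endpoint. At stake is the precision statement on early discharge that a planner of the larger trial would want.

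**Working it through.** **Sample size.** The plan's total is reproduced first: 4 × 6 + 12 = 36 and 5 × 6 + 18 = 48, matching "We propose to enroll at least 36, and up to 48, total Veterans in this pilot RCT". The CCT arm is therefore 4 × 6 = 24 to 5 × 6 = 30 Veterans. (Eighteen TAU participants would fill three groups of six, where the text says two; this does not affect the CCT count.)

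**Event rates.** The documents give no early-discharge rate for this trial. The lower anchor is 0%, from prior CCT initiators. The upper anchor is 10%, from retention above 90%; that is trial retention, so it is only a proxy. Expected events run from 0 to 24 × 0.10 = 2.4, or 30 × 0.10 = 3.0, hence about 0–3. The 2% and 5% rows below are assumptions. The 20% row is a pessimistic value taken from "Retention will be deemed successful if we achieve 80% completion for post-treatment assessments", which concerns assessments, not discharge from CCT.

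**Binomial probabilities.** With independent Veterans, P(0) = (1 − p)^n. Each cell gives n = 24 / n = 30.

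| True rate | Expected events | P(0 events) | P(3 or fewer) |
|---|---|---|---|
| 2% | 0.48 / 0.60 | 61.6% / 54.5% | 99.9% / 99.7% |
| 5% | 1.2 / 1.5 | 29.2% / 21.5% | 97.0% / 93.9% |
| 10% | 2.4 / 3.0 | 8.0% / 4.2% | 78.6% / 64.7% |
| 20% | 4.8 / 6.0 | 0.47% / 0.12% | 26.4% / 12.3% |

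At a true rate of 0%, P(0) is 100%. The 0–3 figure is a range of expected counts: at 10%, four or more events still occur with probability 1 − 0.786 = 21% or 1 − 0.647 = 35%.

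**Behaviour of the mixed model.** An intercept-only random-intercept logistic model was fitted by maximum likelihood to 4,000 simulated datasets per setting (4 or 5 groups of six). The true between-group SD on the logit scale was assumed to be 0 or 1. Ranges run over group number and SD.

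| True rate | No finite estimate | Group variance estimated at zero | Either |
|---|---|---|---|
| 2% | 53–64% | 32–44% | 95–98% |
| 5% | 23–35% | 49–66% | 82–90% |
| 10% | 5–13% | 52–73% | 64–77% |
| 20% | 0.1–1.8% | 43–76% | about 45–76% |

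The two failures differ. Among datasets with at least one event, the variance is zero in 0.488/(1 − 0.349) = 75% to 0.612/(1 − 0.288) = 86% at a 5% rate. At 10% the range is 0.516/(1 − 0.127) = 59% to 0.728/(1 − 0.046) = 76%. In those cases the fit reduces to an ordinary logistic model with a finite proportion.

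**Exact interval.** Clopper-Pearson limits exist at every count. For 0/n the 95% upper limit is 1 − 0.025^(1/n): 14.2% for n = 24 and 11.6% for n = 30. With three events the limits are 2.7–32.4% (3/24) and 2.1–26.5% (3/30).

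**The case against.** A reader might infer that the plan will yield no usable result on early discharge, and that a main Aim 1 acceptability result is lost. The documents do not support either reading. Participation rates, attendance records and dropout rates are planned, so the observed proportion should be available whatever happens to the model. The numerical criteria in Study Feasibility Analyses concern screening, enrolment and assessment completion. Satisfaction is measured by the CSQ8, and no decision rests on early discharge.

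A reader might also infer that the model will usually be non-estimable. That is too strong. Only zero events removes the finite estimate; at a 5% rate, 71–78% of trials would have at least one event.

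The rates themselves are uncertain. The 0% figure covers Veterans who started CCT in earlier studies, and the plan itself warns that Veterans with and without TBI may differ. It also prepares for Veterans who stop treatment, so early discharge could be higher here. Finally, a group-level random effect with one outcome per Veteran is an inference, since the plan specifies neither.

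All of this stands, and it lowers the severity. It does not rescue the method: the mixed model is still the only one tied to early discharge, no interval is planned elsewhere, and no rule covers zero events.

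**Conclusion.** The point holds as a minor one. The named model does not match the data it will receive: 24–30 Veterans, 4–5 groups and about 0–3 expected events at the team's earlier rates. It cannot report a zero count, whose probability runs from 55–62% at an assumed 2% rate to under 0.5% at 20%. With a few events it often collapses to a simple proportion. What is lost is mainly a valid interval, not the proportion itself. The conclusion rests on retention serving as a proxy for early discharge, on independence for the binomial figures, and on the CCT group being the random effect. Because the simulation's model form and between-group SDs are assumptions, its percentages are indicative.

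**What to change.** Replace the sentence so that the primary summary of early discharge is the observed proportion among CCT Veterans with an exact (Clopper-Pearson) 95% interval, accompanied by counts by CCT group and by session number. State how early discharge is counted and whether the denominator is all Veterans randomised to CCT or only those who started.

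Add that the interval treats Veterans as independent and ignores clustering within groups of six; positive correlation within groups would make it too narrow. The counts by group let a reader judge this.

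Keep a mixed model only as exploratory, above a minimum event count fixed in advance. Five or six events would not be a safe threshold: at a 20% rate (4.8–6.0 expected events) the simulated variance was still zero in 43–76% of datasets.

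The cost is a few sentences in the analysis plan. No new data are needed, because attendance is already to be recorded. The one small downside is the independence assumption.

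### The primary multilevel model is not said to use the baseline score for adjustment; specifying this would gain modest precision at best, at almost no cost

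*Combined protocol and SAP*

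**What the plan says.** Two parts of the combined protocol and SAP define the between-arm analysis. Data Analysis promises intention-to-treat analyses to "compare change from baseline to 3-month follow-up within and between groups". Clinical and Functional Outcome Analyses says that "Primary outcome analyses will be multilevel models to compare the change over time" in cognitive, mental health, functioning and quality-of-life outcomes. It adds a conditional fallback: "If the sample size is too small to run multilevel models", then "we will run alternative methods such ANOVAs which are more feasible with smaller samples".

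The baseline value of the outcome is not given a role in either model. Baseline is mentioned for description ("we will compare participant characteristics at baseline by group (CCT vs. TAU"), which adjusts nothing. Covariance analysis appears once, for a different purpose: "Multilevel models or repeated measures analysis of covariance (ANCOVA) models will examine potential moderators". The moderators listed there do not include the baseline score of the outcome being analysed.

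The data for an adjusted analysis will exist. Enrollment and Assessment Procedures sets assessments at baseline, about 3 months and 6 months. Informed Consent & HIPAA Authorization lists the baseline assessment before randomisation.

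**The concern.** A model described only as comparing change over time is often fitted with group, time and their interaction, and with baseline means left free in each arm. With complete data, the 3-month interaction is then exactly the difference in mean change. That estimator subtracts the baseline with a fixed coefficient of one, whatever the actual correlation between visits. A model that constrains the baseline means, or regresses follow-up on baseline, estimates the coefficient and is usually more precise when baseline is measured before allocation.

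This matters because of how the estimates will be used. The section on study setting and sample size names effect-size estimation among the primary purposes, although Clinical and Functional Outcome Analyses calls it an additional goal. The latter section carries the estimates into the power and sample size of the next trial, alongside the earlier mild TBI data. With as few as 12 TAU Veterans, chance baseline imbalance is likely, and the choice of estimator affects how well it is handled.

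**Working it through.** The plan gives no power calculation, SD or effect size, so there is no figure of its own to reproduce. The check compares the two estimators.

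**Inputs from the documents.** Total 36 to 48 Veterans (study setting and sample size). CCT 24 to 30, as four to five groups of six, and TAU 12 to 18 (Inclusion/Exclusion Criteria). So 24 + 12 = 36 and 30 + 18 = 48. Whole groups of six are randomised (Randomization and Blinding).

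**Assumptions, not in the documents.** SD = 1 at each visit. Correlation between baseline and 3 months r = 0.5 to 0.8, with 0.9 as an extreme. Complete data.

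**Formulas, no clustering.** Let k = 1/n(CCT) + 1/n(TAU).
- Difference in change: variance = 2(1 − r)k.
- Baseline-adjusted difference: variance = (1 − r²)k × [1 + 1/(N − 4)]. The bracket is the cost of estimating the slope: 1/32 = 3.1% at N = 36 and 1/44 = 2.3% at N = 48.
- Ratio, adjusted to change = [(1 + r)/2] × [1 + 1/(N − 4)].

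**Worked case.** At N = 36, k = 1/24 + 1/12 = 0.125. At r = 0.5 the change variance is 2 × 0.5 × 0.125 = 0.125 (SE 0.354). The adjusted variance is 0.75 × 0.125 × 1.03125 = 0.0967 (SE 0.311). The ratio is 0.773. Half-widths use t with N − 2 df (change) or N − 3 df (adjusted).

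| N | r | Variance ratio | 95% half-width, change (SD) | 95% half-width, adjusted (SD) |
|---|---|---|---|---|
| 36 | 0.5 | 0.773 | 0.72 | 0.63 |
| 36 | 0.7 | 0.877 | 0.56 | 0.52 |
| 36 | 0.8 | 0.928 | 0.45 | 0.44 |
| 36 | 0.9 | 0.980 | 0.32 | 0.32 |
| 48 | 0.5 | 0.767 | 0.60 | 0.53 |
| 48 | 0.7 | 0.869 | 0.47 | 0.43 |
| 48 | 0.8 | 0.920 | 0.38 | 0.36 |
| 48 | 0.9 | 0.972 | 0.27 | 0.27 |

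**Does the multilevel form change this?** A generalised least squares calculation for three visits at 24:12, with variances treated as known, gives the 3-month contrast an SE of 0.354, 0.274 and 0.224 (r = 0.5, 0.7, 0.8) when baseline means are free. These equal the change-score SEs. Constraining the baseline means gives 0.306, 0.252 and 0.212, or variance ratios of 0.75, 0.85 and 0.90 before the slope penalty. So a multilevel model does not recover the precision by itself; the constraint does.

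**Stable differences between the groups of six.** Veterans fill a group as they enrol, so groups may already differ at baseline and keep that difference. A change score cancels such a difference; adjustment removes only part of it. Simulated variance ratios (adjusted to change), with the same group effect at both visits:

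| Groups (CCT + TAU) | Assumed ICC | r = 0.5 | r = 0.7 | r = 0.8 | r = 0.9 |
|---|---|---|---|---|---|
| 4 + 2 | 0.05 | 0.85 | 0.93 | 0.97 | 1.00 |
| 4 + 2 | 0.10 | 0.93 | 0.98 | 1.00 | 1.02 |
| 5 + 3 | 0.05 | 0.84 | 0.92 | 0.96 | 0.99 |
| 5 + 3 | 0.10 | 0.92 | 0.96 | 1.00 | 1.01 |

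A fresh simulation for this write-up agreed to within about 0.02. For r from 0.5 to 0.8 the gain therefore runs from about 16% down to 1% or less. At r = 0.9 it is nil, or a loss of up to about 2%.

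**The case against.** The strongest reply is that silence is not loss. A model with baseline means held equal also compares change over time, so the stated wording is compatible with the better analysis. That stands: the gap is an unspecified choice.

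The second reply is that the gain hardly matters here. Half-widths of 0.36 to 0.63 SD after adjustment are still too wide to size a trial alone, and the plan itself says that pilot effect sizes should not be the sole source and disclaims power. This also stands, and it limits the point to a cheap improvement. It does not justify leaving the model open.

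The third reply is that the size of the gain rests on an assumed correlation and on how the groups behave. The second table bears this out: the no-clustering range cannot be quoted as if it were safe. The half-widths also use individual-level degrees of freedom although only six to eight groups would be randomised.

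A fourth reply is that the SD used to standardise the effect may matter more. At r = 0.8 the change SD is √(2 × 0.2) = 0.63 of the raw SD, so a raw 0.5 SD becomes 0.5/0.63 = 0.79. That is correct, but it is a separate choice and does not affect which estimator is more precise.

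A reader might also infer that the ANOVA fallback breaks the intention-to-treat commitment, because the plan "though will not conduct multiple imputation or other missing data techniques for this pilot study" yet promises "analyzing data from all randomized participants assigned to CCT versus TAU groups, rather than only including completers". The documents do not support this. The fallback is conditional and its type is unstated, the named contrast needs only baseline and 3 months, and completers may mean those who completed treatment.

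**Conclusion.** The point holds as a free improvement. The plan describes a between-arm comparison of change and nowhere says that baseline is adjusted for or constrained. An ordinary group-by-time fit would leave precision unused.

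The size is modest and conditional. Under assumed r of 0.5 to 0.8 and no group-level variance, the variance falls by about 7-23%. With stable differences between the groups of six at an assumed ICC of 0.05 to 0.10, the reduction is about 16% at best and 1% or less at worst. Near r = 0.9 with such differences there is no gain, or a loss of up to about 2%.

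A reader might go further and conclude that the trial is committed to an inefficient analysis, or that its effect estimates will be biased. Neither follows. The wording permits a constrained model, and nothing in the check shows bias. Only the precision of the estimate is at issue.

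**What to change.** In Clinical and Functional Outcome Analyses, state that the primary multilevel model uses all available visits, with baseline means constrained equal across arms. Adjusting follow-up scores for the baseline value of the same outcome is an acceptable alternative. Replace the ANOVA fallback with an ANCOVA adjusted for that same baseline value. Align the sentence in Data Analysis so that both places describe one estimator.

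The cost is wording only, with no new data or visits. The statistical price is one degree of freedom and about 2-3% of variance for estimating the slope, which is already included in the no-clustering figures above. Fixing the model before the data are seen also removes the freedom to choose between change-score and adjusted results afterwards.
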